#### 7.2.3 Description

Nivolumab Injection, 100 mg/vial (10 mg/mL) is a clear to opalescent, colorless to pale, yellow liquid; light (few) particulates may be present. The drug product is a sterile, nonpyrogenic, single-use, isotonic aqueous solution formulated at 10 mg/mL in sodium citrate, sodium chloride, mannitol, diethylenetriamine pentacetic acid and polysorbate 80 (Tween™ 80), pH 6.0 and includes a 0.7-mL overfill to account for vial, needle, and syringe (VNS) holdup. It is supplied in 10-cc type I flint glass vials, stoppered with butyl rubber stoppers and sealed with aluminum seals.

#### 7.2.4 Packaging and Labeling Information

Clinical supplies will be affixed with a clinical label in accordance with regulatory requirements. Open-label cartons will be supplied with 5 vials per carton.

#### 7.2.5 Preparation

Nivolumab injection should be infused undiluted (10 mg/mL) or be diluted with 0.9% Sodium Chloride Injection, USP or 5% Dextrose Injection, USP to prepare an infusion with a final concentration ranging from 1 mg/mL to 10 mg/mL. The total volume of infusion must not exceed 160 mL. Care must be taken to assure sterility of the prepared solution as the product does not contain any anti-microbial preservative or bacteriostatic agent. No incompatibilities between nivolumab and polyolefin bags have been observed. Recommended safety measures for preparation and handling of nivolumab include laboratory coats and gloves. Detailed instructions on the preparation of nivolumab for administration will be provided in the Procedures Manual.

#### 7.2.6 Storage

Clinical supplies must be stored in a secure, limited-access location. Nivolumab vials must be stored at a temperature of 2°C to 8°C and should be protected from light and freezing. If stored in a glass front refrigerator, vials should be stored in the carton. Receipt and dispensing of trial medication must be recorded by an authorized person at the trial site.

Clinical supplies may not be used for any purpose other than that stated in the protocol.

#### 7.2.7 Stability

The administration of nivolumab infusion must be completed within 24 hours of preparation. If not used immediately, the infusion solution may be stored under refrigeration conditions (2°-8°C, 36°-46°F) for up to 24 hours, and a maximum of 8 hours of the total 24 hours can be at room temperature (20°-25°C, 68°-77°F) and room light. The maximum 8-hour period under room temperature and room light conditions includes the product administration period.

#### 7.2.8 Route of Administration

Nivolumab is to be administered as a 30 minute IV infusion, using a volumetric pump with a 0.2/0.22 micron in-line filter at the protocol-specified dose. It is not to be administered as an IV push or bolus injection. At the end of the infusion, flush the line with a sufficient quantity of normal saline.

#### 7.2.9 Subject Care Implications

The overall safety experience with nivolumab is based on experience in approximately 1500 subjects as either a monotherapy or in combination with other therapeutics. In general for monotherapy, the safety profile is similar across tumor types. The one exception is pulmonary inflammation AEs which may be numerically greater in subjects with NSCLC possibly because in some cases it can be difficult to distinguish between nivolumab-related and unrelated causes of pulmonary symptoms and radiographic changes. The most frequently reported treatment related AE is fatigue which is almost always low grade.

Most related AEs are thought to be due to the effects of inflammatory cells on specific tissues. A variety of PTs have been used to describe similar kinds of organ-related AEs with the result being that AE frequency tables organized by PTs can lead to underestimation of the frequency of similar kinds of organ-related AEs. To address this issue, select AE categories were created. Select AE categories group together the most common and impactful PTs by organ category. These categories include the following: pulmonary, gastrointestinal, hepatic, dermatologic, endocrine, and renal AEs. It is also useful to consider the management of nivolumab-related AEs by organ category as the diagnostic workup often requires excluding other potential diagnoses and when appropriate instituting specific management principles as outlined in this protocol and Appendix 2.

#### 7.2.10 Returns and Reconciliation

The investigator is responsible for keeping accurate records of the clinical supplies received from BMS or designee, the amount dispensed to, and returned by the subjects and the amount remaining at the conclusion of the trial.

Upon completion or termination of the study, all unused and/or partially used investigational product will be destroyed at the site per institutional policy. It is the Investigator's responsibility to arrange for disposal of all empty containers, provided that procedures for proper disposal have been established according to applicable federal, state, local and institutional guidelines and procedures, and provided that appropriate records of disposal are kept. BMS will be notified of all destruction of

study drug.

### **7.3 Ipilimumab**

#### **7.3.1 Agent Accountability**

The IND sponsor or the Sponsor's representative shall take responsibility for and shall take all steps to maintain appropriate records and ensure appropriate supply, storage, handling, distribution and usage of investigational product in accordance with the protocol and any applicable laws and regulations.

#### **7.3.2 Mode of Action**

Ipilimumab is a fully human immunoglobulin (IgG1κ) that is specific for the CTLA-4 antigen expressed on a subset of activated T-cells. CTLA-4 interaction with the B7 molecule, one of its ligands expressed on professional antigen presenting cells, can down-regulate T-cell response. Ipilimumab is, thought to act by blocking the interaction of CTLA-4 with the B7 ligand, resulting in a blockade of the inhibitory effect of T-cell activation. The CTLA-4/B7 creates the interaction.

#### **7.3.3 Description**

Ipilimumab injection, 200 mg/40 mL (5 mg/mL), is formulated as a clear to slightly opalescent, colorless to pale yellow, sterile, nonpyrogenic, single-use, isotonic aqueous solution that may contain particles. Ipilimumab injection, 200 mg/40 mL, is supplied in 50-cc Type I flint glass vials, stoppered with gray butyl stoppers and sealed with aluminum seals. The drug product is formulated at a concentration of 5 mg/mL at a pH of 7.0. in sodium chloride, TRIS-hydrochloride, diethylenetriamine pentacetic acid, mannitol, polysorbate 80 (TweenTM 80), and water, and includes a 0.7-mL overfill to account for vial, needle, and syringe (VNS) holdup.

#### **7.3.4 Packaging and Labeling Information**

Clinical supplies will be affixed with a clinical label in accordance with regulatory requirements. Open-label cartons will be supplied with 5 vials per carton.

#### **7.3.5 Preparation**

The drug can be diluted with 0.9% normal saline or 5% Dextrose Injection to concentrations between 1 mg/mL and 4 mg/mL. It is not to be administered as an IV push or bolus injection. Care must be taken to assure sterility of the prepared solutions, since the drug product does not contain any antimicrobial preservatives or bacteriostatic agents. Recommended safety measures for preparation and handling of ipilimumab include laboratory coats and gloves. Detailed instructions on the preparation of ipilimumab for administration will be provided in the Pharmacy Manual.

#### **7.3.6 Storage**

Clinical supplies must be stored in a secure, limited-access location. Ipilimumab vials must be stored at a temperature of 2°C to 8°C and should be protected from light and freezing. If stored in a glass front refrigerator, vials should be stored in the carton.

Receipt and dispensing of trial medication must be recorded by an authorized person at the trial site.

Clinical supplies may not be used for any purpose other than that stated in the protocol.

#### 7.3.7 Stability

The administration of ipilimumab infusion must be completed within 24 hours of preparation. If not used immediately, the infusion solution may be stored in IV infusion bags (PVC, non-PVC/non-DEHP) or glass infusion containers under refrigeration conditions (2°-8°C, 36°-46°F) with protection from light and from freezing or at temperature/room light (20-25°C, 68-77°F) for up to 24 hours. This would include any time in transit and the total time for infusion.

#### 7.3.8 Route of Administration

Ipilimumab is to be administered as a 30 minute IV infusion, using a volumetric pump with a 0.2 to 1.2 micron in-line filter at the protocol-specified dose. It is not to be administered as an IV push or bolus injection. At the end of the infusion, flush the line with a sufficient quantity of normal saline (approximately 30-50mL).

#### 7.3.9 Subject Care Implications

The overall safety experience with ipilimumab is based on experience in approximately 19,500 subjects as either a monotherapy or in combination with other therapeutics. The safety profile of ipilimumab is generally consistent across these trials with a) the majority adverse events (AEs) being inflammatory in nature, which is consistent with the proposed mechanism of action of ipilimumab; b) the same types of such immune-mediated events in the gastrointestinal (GI) tract (eg, diarrhea and colitis), skin (eg, pruritus and rash), liver (eg, transaminase elevations), endocrine glands (including the thyroid, pituitary and adrenal glands, manifested by hypothyroidism, hypophysitis with hypopituitarism, or adrenal insufficiency, respectively), and nervous system (eg, motor neuropathy with or without sensory neuropathy) being reported; and c) most of these events being manageable using symptomatic or immuno-suppressive therapy as recommended through detailed diagnosis and management guidelines as outlined in this protocol and **Appendix 2**.

#### 7.3.10 Returns and Reconciliation

The investigator is responsible for keeping accurate records of the clinical supplies received from BMS or designee, the amount dispensed to, and returned by the subjects and the amount remaining at the conclusion of the trial.

Upon completion or termination of the study, all unused and/or partially used investigational product will be destroyed at the site per institutional policy. It is the Investigator's responsibility to arrange for disposal of all empty containers, provided that procedures for proper disposal have been established according to applicable federal, state, local and institutional guidelines and procedures, and provided that appropriate records of disposal are kept. BMS will be notified of all destruction of study drug.

## 8. Correlative Studies collection and handling

Correlative studies will be performed to evaluate immune system activation and for potential biomarker identification. A variety of factors that could potentially predict clinical response to nivolumab and ipilimumab will be investigated in tumor specimens and in peripheral blood obtained prior to first dose of study drug, on study and potentially progression, as outlined in the **Study Calendar**. Baseline and on treatment tumor assessment of response, immune reactivity and gene expression will be performed on all patients during the second stage of this trial. Plasma samples will be collected on all patients for ctDNA and immunogenicity studies.

### 8.1 Tumor Tissue Studies

Archival or recently collected FFPE tumor tissue (in the form of paraffin embedded block or unstained slides, as described in **Section 8.1.1**) collected prior to enrollment, will be requested for all patients participating in this study.

Pre-treatment and on-treatment biopsies of patients on Stage 2 will also be collected as per the **Study Calendar**. A biopsy sample of subjects who experience progression at any time while on treatment is optional, but strongly encouraged for the purposes of understanding mechanisms of resistance to therapy.

Several analyses will be completed and are described briefly below.

#### 8.1.1 Tumor Tissue Handling

A formalin-fixed, paraffin-embedded (FFPE) tumor tissue block (preferred) or 10 unstained slides of tumor sample (archival or recent) for biomarker evaluation must be available and submitted for correlative studies in order for a subject to be enrolled as described in the **Laboratory Manual**. If fewer than 10 slides are available, the Principal Investigator may still approve enrollment of subjects upon review of the case. Excisional, incisional or core needle biopsies are strongly preferred, however samples collected via endobronchial ultrasound (EBUS) guided biopsy (using a 22g needle or larger) and transbronchial lung biopsy (TBLB) are acceptable. In certain cases, the Principal Investigator may approve submission of samples collected via other methods.

If a new biopsy is taken (i.e. no archival tissue is available), up to 5 core biopsies are recommended at baseline. Otherwise, up to 4 core biopsies should be collected at baseline and at other time points per the Study Calendar. An assessment of biopsy quality by a pathologist is encouraged at the time of the procedure. The tumor tissue that is obtained from these biopsies will be allocated to FFPE, fresh frozen and for RNA later as described in the **Laboratory Manual**. The investigator, in consultation with the radiology staff, must determine the degree of risk associated with the procedure and find it acceptable. Biopsies may be done with local anesthesia or conscious sedation. Institutional guidelines for the safe performance of biopsies should be followed. Excisional biopsies may be performed to obtain tumor biopsy samples. Invasive procedures that require general anesthesia should not be performed to obtain a biopsy specimen. However, if a surgical procedure is performed for a clinical indication, excess tumor tissue may be used for research purposes with the consent of the subject.

A pathology report should be provided with tumor samples.

#### 8.1.2 Tumor microenvironment (TME) analysis by IHC

Immunohistochemistry (IHC) will be used to assess the number and composition of immune infiltrates in order to define the immune cell subsets present within FFPE tumor tissue before, during and after exposure to therapy. These IHC analyses will include, but not necessarily be limited to, the following markers relevant to the PD-L1/PD-1 and CTLA-4 pathways will be performed on FFPE slides of treated patients: densities and distribution of effector T cells (Teff) including CD8, CD45RO, CXCR3 and CD69+ cells, expression of immune suppressive signals including PD-1, PD-L1, PD-L2, LAG3, TIM3, and IDO1, immune activation signals including CD137(4-1BB), 4-1BBL, OX40, OX40L, CD40, and CD40L on T cells and macrophages, and the expression of T helper cell differentiation markers including Tbet (for Th1), GATA3 (for Th2), ROR  $\gamma$  T (for Th17), and Foxp3 (for Treg) will be assessed as previously described (Lutz et al. 2014).

Quantification of IHC on immune markers will be conducted by Aperio's Immune Analysis Software Program as described previously (Lutz et al. 2014) and will be supervised by an on-site pathologist. A specific evaluation will be whether the combination of nivolumab and ipilimumab collaboratively suppress the Treg pathway and enhance effector T cell infiltration.

#### 8.1.3 Genomic assessment and gene expression

DNA or RNA extracted from tumor provided may be used for whole genome or exome sequencing to identify mutational load and transcriptional expression. Sequencing of pre- and on-treatment biopsies may be compared to evaluate for predictors of response or resistance. Gene expression will be quantified by nanostring assays to assess whether the combination of nivolumab and ipilimumab influences immune cells within the tumor microenvironment. The gene expression signatures listed in **Table 4** and the signature found to correlate with responses to the study treatment will be evaluated.

Next-generation sequencing may be used to examine the TCR repertoire in peripheral blood lymphocytes (PBL) and TIL from FFPE sections from the pre- or on-treatment biopsies, to identify if TCR clonal expansion is taking place. TCR repertoires in PBL vs TIL may also be compared from the same patients to identify any T cell clones that are induced or expanded in PBL by combination treatment and also enriched in TIL. This data may be used to determine if T cells in PBL and TIL undergo clonal expansion following treatment, and if so, whether the T cell clones traffic to the carcinoid TME.

Nonsynonymous missense mutations identified may be used to predict mutant peptides and generate a neoantigen signature for each tumor using a computational pipeline we have developed. A separate targeted capture and sequencing analysis of the T cell receptor may be performed to assess T cell clonality.

**Table 4.** Immune-Related Gene Expression Signatures (27).

IFN $\gamma$	Expanded Immune	TCR Signaling	De Novo
IDO1	CD3D NKG7	CD27	IKZF3 SAMHD1 CD38
CXCL10	IDO1 HLA-E	TIGIT	HLA-DPB1 TIGIT
CXCL9	CIITA CXCR6	CD8A	CRTAM
HLA-DRA	CD3E LAG3	CD3D	CD27 IL2RB CD8A
STAT1	CCL5 TAGAP	GRAP2	AMICA1 TARP CXCL9
IFNG	GZMK CXCL10	LCK	CD74 CD3D HLA-C
	CD2 STAT1	PTPRCAP	LY9 CD3G GPR18
	HLA-DRA GZMB	CD4	CD4 HLA-B IL18
	CXCL13	CCL5	HLA-DRA IGJ CX3CR1
	IL2RG	IL2RB IKZF3	B2M IRF1 CXCL10
	EOSMES	CD3G CD74	IGSF6 BST2 SIT1
			FASLG PTPN7 LCK

IFN = interferon; TCR = T-cell receptor

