### **3. PATIENT SELECTION**

#### **3.1 Eligibility Criteria**

- 3.1.1 Subjects with histologically confirmed advanced, progressive, well-differentiated nonfunctional NET of the pancreas, lung or gastrointestinal (GI) tract per the 8th International Association for the Study of Lung Cancer classification (IASLC) or the American Joint Committee on Cancer (AJCC) Staging Handbook, 7th edition. Progression must be documented over the prior 12 months.
- 3.1.2 Measurable disease by CT or MRI per RECIST 1.1 criteria (Appendix 3); radiographic tumor assessment performed within 28 days before treatment. Target lesions may be located in a previously irradiated field if there is documented (radiographic) disease progression in that site after the completion of radiation therapy.
- 3.1.3 Prior therapy, including everolimus, octreotide, surgery, chemoradiation, is all permitted after being properly noted. This prior therapy must have been completed at least 28 days prior to study enrollment.
- 3.1.4 Patients with lung NETs must have progressed after at least 1 line of therapy. Patients with GI NETs must have had at least 2 lines of prior therapy.
- 3.1.5 Subjects are to have tumor tissue sample available at central lab for PD -L1 IHC testing during the screening period. Subjects can initiate therapy before the result of IHC testing.
- 3.1.6 (Stage 2 only) Subjects must be willing to undergo 2 sets of core needle biopsies (pre-treatment and at 6-8 weeks on therapy) if there are lesions amenable to biopsy. Subjects without a lesion amendable to biopsy will still be permitted to enroll provided they have an archival tumor sample for PD-L1 IHC testing. An optional core biopsy will be requested at progression.

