	
a: LDH, AST, ALT, ALP, T. bili, BUN or serum urea level, creatinine, albumin, Ca, Mg, Na, K, Cl, phosphate, glucose, amylase, lipase, TSH, Free T4, Free T3, within 14 days prior to first dose.
 
b: Hep B/C (HBV sAg, HCV antibody or HCV RNA), within 28 days prior to first dose.
 
c: Thyroid Function Testing to be evaluated every 6 weeks
 
d: A serum or urine pregnancy testing is required prior to study enrollment/registration, also within 24 hours prior to D1 (and extension to 72 hours may be granted if unable to obtain within 24 hrs). Must be reassessed every 4 weeks.
 
e: CT scan of the chest and other relevant sites as well as MRI brain with gadolinium (or CT scan brain with contrast if MRI is contraindicated) will be performed <math>\leq</math> 4 weeks prior to the start of therapy. For subsequent scans, may be done within +/- 7 days of intended visit.
 
f: Within 72 hrs prior to dosing to include CBC w/ differential, AST, ALT, ALP, T. bili, BUN or serum urea level, creatinine, albumin, Ca, Mg, Na, K, Cl, LDH, phosphate, glucose, amylase, lipase, TSH (with reflexive Free T4 and Free T3). Note: C1D1 labs do not need to be repeated if they were performed within 14 days of dosing.
 
g: All treatments may be performed +/- 2 days of the intended treatment administration dates schedule for all cycles.
 
h: Recent sample or archival obtained. One (1) formalin-fixed paraffin embedded tumor tissue block or a minimum of 10 unstained tumor tissue sections are acceptable.
 
i: Mandatory fresh tissue will be collected for biomarker studies at baseline and on treatment (week 6-8) for patients enrolled in the second stage of the study.
 
j: Immunogenecity samples should be collected just before the administration of the first drug (preferably within 30 minutes).
 
k: Adverse event evaluation as per Common Terminology Criteria for Adverse Events (CTCAE) version 4.0
 
l: Survival follow-up may be done via phone call for survival status and subsequent therapy
 
m: CT if the subject came off study for reasons other than PD
 
n: EOT assessments do not need to be repeated if performed within 14 days
 
o: In order to minimize the need for research-only in-person visits, telemedicine visits may be substituted for in-person clinical trial visits or portions of clinical trial visits where determined to be appropriate and where determined by the investigator not to increase the participant's risks. Prior to initiating telemedicine for study visits the study team will explain to the participant, what a telemedicine visit entails and confirm that the study participant is in agreement and able to proceed with this method. Telemedicine acknowledgement will be obtained in accordance with the Guidance for Use of Telemedicine in Research. In the event telemedicine is not deemed feasible, the study visit will proceed as an in-person visit. Telemedicine visits will be conducted using HIPAA compliant method approved by the Health System and within licensing restrictions.
								

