# **11. MEASUREMENT OF EFFECT**

## **11.1 Antitumor Effect**

For the purposes of this study, patients should be re-evaluated every 6 weeks. In addition to a baseline scan, confirmatory scans will also be obtained 6 (not less than 4) weeks following initial documentation of an objective response.

Response and progression will be evaluated in this study using the new international criteria proposed by the revised Response Evaluation Criteria in Solid Tumors (RECIST) guideline (version 1.1). Changes in the largest diameter (unidimensional measurement) of the tumor lesions and the shortest diameter in the case of malignant lymph nodes are used in the RECIST criteria.

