### 12.3.2 Secondary Endpoints

Secondary endpoints include safety and tolerability of study treatment; PFS, DCR, DOR and OS in the all treated subjects population.

Safety and tolerability objectives will be measured by the incidence of adverse events, serious events, deaths, and laboratory abnormalities. Dates and duration of study treatment delays will also be described.

PFS is defined as the time from first dose to the date of the first documented tumor progression (per RECIST 1.1), or death due to any cause. Clinical deterioration in the absence of radiographic evidence is not considered progression for purposes of determining PFS. Subjects who die without a reported prior progression will be considered to have progressed on the date of their death. Subjects who did not progress or die will be censored on the date of their last evaluable tumor assessment.

Subjects who did not have any on study tumor assessments and did not die will be censored on the first dosing date. Subjects who started any palliative local therapy or subsequent anti-cancer therapy without a prior reported progression will be censored at the last evaluable tumor assessment prior to initiation of the palliative local therapy or subsequent anti-cancer therapy, whichever procedure occurred first. PFS rate at 6 months is defined as the rate from Kaplan-Meier estimate 6 months after first dosing date.

Disease control rate is defined as the number of subjects with a BOR (per RECIST v1.1 criteria) of confirmed CR or PR or SD (stable disease), divided by the number of treated subjects.

Duration of response will be summarized among subjects with objective response in and is measured from the time at which the criteria for objective response are first met until the date of a progression event (according to the definition of PFS). Subjects with objective response who does not have a progression event will be censored at the same time they were censored under the definition of PFS.

Overall survival is defined as the time from first dosing date to the date of death. A subject who has not died will be censored at last known alive date. The overall

survival rate at 6 months is the rate from Kaplan-Meier estimate 6 months after dosing date.

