### 12.3.3 Exploratory Endpoint(s)

All biomarker measures, T-cell response, immune phenotype and inflammatory response evaluation will be listed, tabulated, and where appropriate plotted. Tumor tissue IHC, functional analysis and genomic analysis will be listed, tabulated and where appropriate plotted. For the continuous data, summary statistics and the corresponding changes (or percent changes) from baseline will be provided at each time-point of assessment as well as for the changes from baseline to the peak value. Categorical data will be summarized as appropriate. Subjects will be grouped by dose level or clinical response. As this is an open-label study without a control treatment, statistical analyses will be done to aid in the understanding of the results. The associations of biomarkers with dose, clinical response, or time-to-event endpoints may be assessed using the appropriate statistical methods (analysis of variance [ANOVA], categorical, or survival model), depending on the endpoint. Correlation of baseline expression levels or changes in expression levels with response or time-to-event endpoints will identify potential responsive (or resistant) subgroups.

The ctDNA and IMG objectives will be measured from serum concentration. Response characteristics will be summarized descriptively and are further described in the statistical analysis plan.

Other exploratory endpoints are discussed in details in the statistical analysis plan.

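### Change in tissue at week 6-8 is to be related to response and to PFS/OS from first dose, although the first scan usually precedes that biopsy and no landmark is set

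*Combined protocol and SAP*

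**What the plan says.** The combined protocol and SAP makes these statements.

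- **When tissue is taken.** Section 9, footnote i: "Mandatory fresh tissue will be collected for biomarker studies at baseline and on treatment (week 6-8) for patients enrolled in the second stage". Section 3.1.6 limits this to subjects with a lesion that can be biopsied, and makes a biopsy at progression optional.
- **When response is assessed.** Section 11.1: "patients should be re-evaluated every 6 weeks". A cycle is 42 days (Section 4.1.2), the calendar puts the on-treatment scan in the Cycle 2 block, and footnote e allows 7 days either way.
- **How the tissue is used.** Section 8.1.3: "Sequencing of pre- and on-treatment biopsies may be compared to evaluate for predictors of response or resistance". Section 12.3.3: "Correlation of baseline expression levels or changes in expression levels with response or time-to-event endpoints will identify potential responsive (or resistant) subgroups".
- **Where the clocks start.** Section 12.3.2: "PFS is defined as the time from first dose to the date of the first documented tumor progression". OS also starts at first dose. Best overall response is collected from baseline (Section 12.3.1).
- **Progression and treatment.** Section 4.9 lists progression as a reason for removal. Sections 4.10 and 5.3 allow treatment to continue beyond it under stated conditions.

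The text names no landmark, no time-dependent covariate, no rule on the order of scan and biopsy, and no handling of subjects without a paired sample. Section 12.3.3 refers further exploratory detail to a statistical analysis plan; the supplied text contains nothing on these points.

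**The concern.** A predictor has to be measured before the outcome it predicts. Here the change score is complete only at the second biopsy, while the outcome has been accruing since first dose and has usually been read once by then. There are three consequences.

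1. **Response.** A tumor that met response criteria at the week-6 scan has already shrunk when it is sampled. A marker that merely reflects shrinkage can then look like a predictor of it.
2. **Progression followed by biopsy.** If a subject progresses at week 6, stays on treatment and is then biopsied, the tissue may show the effect of progression. Entered in a survival model from first dose, it appears to forecast an event that has already happened.
3. **Progression without biopsy.** Other early progressors will have no second sample. Everyone in the paired set has then survived progression-free to the biopsy, so PFS read from that set is too favorable as a description of all treated subjects.

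At stake is what may be concluded from a required on-treatment biopsy in at most 36 subjects, with perhaps five responders.

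**Working it through.** **Number of subjects.** Section 12.2 gives a two-stage design: 20 subjects, stop if 1 or fewer respond; 56 in total, reject the regimen if 4 or fewer respond.

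- At p = 0.05, early termination = 0.95^20 + 20 x 0.05 x 0.95^19 = 0.736.
- Expected N = 20 + (1 - 0.7358) x 36 = 29.51.
- Exact type I error is 0.097, and type II error at p = 0.15 is 1 - 0.801 = 0.199.

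All four match the plan. Stage 2 therefore has 56 - 20 = 36 subjects, the most that can give mandatory pairs. At 15% ORR that is 0.15 x 36 = 5.4, about 5 responders.

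**Order of scan and biopsy.** The scan window is weeks 5-7 and the biopsy window weeks 6-8. If both dates are spread evenly and independently (assumption), the biopsy comes first only when both fall in weeks 6-7 and in that order: 1/2 x 1/2 x 1/2 = 1/8. The scan comes first in about 88% of subjects.

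**Early events.** Assume exponential PFS, S(t) = 2^(-t/median), with medians of 3.9 and 11 months. These are the placebo and everolimus figures in Section 2.1, used only as a range; they are not design assumptions of this trial. Six weeks = 42/30.4375 = 1.38 months; eight weeks = 1.84 months.

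- By week 6: 1 - 2^(-1.38/3.9) = 22% and 1 - 2^(-1.38/11) = 8%, or 8 and 3 of 36.
- By week 8: 28% and 11%, or 10 and 4 of 36.

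**Effect on the PFS association.** Simulation with 1,500 runs per row: n = 36, six-weekly scans +/- 7 days, biopsy uniform in weeks 6-8, follow-up to week 78, Cox model, and a marker with no true effect on PFS. The shift is the assumed change in the marker, in SD, when the biopsy follows progression.

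| Median PFS (months) | Shift (SD) | Early progressors biopsied | From first dose: p<0.05, HR | Week-8 landmark: p<0.05, HR, mean n |
|---|---|---|---|---|
| 3.9 | 0 | none | 5.3%, 1.00 | 6.4%, 1.00, 28.0 |
| 3.9 | 0.5 | half | 6.8%, 1.06 | 4.7%, 0.99, 28.1 |
| 3.9 | 1 | half | 11.3%, 1.13 | 5.1%, 1.00, 28.1 |
| 3.9 | 1 | all | 20.3%, 1.23 | 5.0%, 1.00, 28.3 |
| 11 | 0 | none | 5.3%, 1.00 | 6.3%, 1.01, 33.1 |
| 11 | 0.5 | half | 5.7%, 1.03 | 6.3%, 1.00, 33.0 |
| 11 | 1 | half | 7.5%, 1.06 | 5.9%, 1.00, 33.0 |
| 11 | 1 | all | 8.8%, 1.13 | 4.3%, 0.99, 33.1 |

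With no shift and half of the early progressors biopsied, rejection is 4.1% and 5.2% from first dose, and 5.2% and 3.7% with the landmark. Over all rows the landmark gives 3.7-6.4%. Simulation error near 5% is sqrt(0.05 x 0.95/1500) = 0.6 percentage points.

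**Effect on absolute PFS.** With no early progressor biopsied, mean simulated median PFS in the sampled set against all subjects is 25.4 against 20.3 weeks, and 57.0 against 51.9 weeks: about 5 weeks longer in both cases.

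**Response.** The documents give no share of responses first seen at week 6. If it is 30-70% (assumption), 0.3 x 5.4 = 1.6 to 0.7 x 5.4 = 3.8, so about 2-4 of 5 responses precede the biopsy.

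**The case against.** **Early progressors can be sampled.** A reader might infer that they never contribute tissue. The documents do not support that: Section 5.3 permits treatment beyond progression, the week 6-8 biopsy is not made conditional on being progression-free, and a progression biopsy may be taken. The inference would also contradict the worry about reversed order, since progression cannot precede a biopsy that was never done. What stands is that some early progressors will lack the sample.

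**Missing early progressors do not distort the marker comparison.** This is right: the hazard ratio stays at 1.00. The inflated PFS in the paired set is also not an estimate the plan proposes, because PFS is estimated in all treated subjects (Sections 12.3.2 and 12.4.2).

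**Only confirmed responses count, so response follows the biopsy.** Confirmation at least 4 weeks after a week 5-7 scan does fall at week 9 or later. But confirmation decides whether a response is counted, not when the tumor shrank. The objection does not remove the reversal.

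**The size for response is assumed.** A reader might quote 11-69% false positives for markers tested against response. That range comes from assuming a 1-2 SD shift and that 30-70% of responses are seen before biopsy, and the plan sets no p<0.05 rule for these markers. It shows the mechanism and is not an estimate for this trial.

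**The wording is guarded and exploratory.** Section 8.1.3 is permissive, Section 12.3.3 speaks of potential subgroups, and Sections 8.1.2 and 8.1.3 already describe pharmacodynamic uses. This limits the weight of the point. The correlation in Section 12.3.3 is nevertheless stated as something that will be done, with no rule on timing.

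**Conclusion.** The point holds in a limited form. As written, the plan can present tissue taken after shrinkage or progression as a predictor of that outcome. For PFS the bias in the hazard ratio arises only when post-progression biopsies enter the model and progression alters the marker. The 8-20% false-positive range rests on an assumed 1 SD shift, on half or all early progressors being biopsied, and on borrowed medians of 11 and 3.9 months; at 0.5 SD with half biopsied it is 6-7%. For response the reversal is clear from the timing, but its size cannot be estimated from the documents.

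The primary ORR test, the two-stage stopping rule, the secondary endpoints and the safety analyses are not affected. This is a cheap improvement to an exploratory analysis. It would be unnecessary if a separate statistical analysis plan already contains such a rule.

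**What to change.** Add to Sections 8.1.3 and 12.3.3:

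1. Claims of prediction use pre-treatment tissue. Change to week 6-8 is reported as a pharmacodynamic result.
2. Where change is related to PFS or OS, include only subjects alive and progression-free at the biopsy date, or at a week-8 landmark, and count time from then.
3. Where change is related to response, call it an association and show for each responder whether the response was first documented before or after the biopsy. Give the analysis limited to responses first seen after biopsy as a sensitivity analysis.
4. Report stage-2 subjects without a paired sample by reason and outcome.

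No visit or procedure is added; the biopsy and scan dates only need to be set against each other. The landmark loses about 36 - 33 = 3 subjects at a median of 11 months and 36 - 28 = 8 at 3.9 months.

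The restriction in item 3 should remain a sensitivity analysis because it could remove 2-4 of about 5 responders. With 26 non-responders and a true 1 SD difference, the power of a two-sided t-test falls from about 0.51 with 5 responders to 0.35 with 3 and 0.26 with 2.
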